AR	Adverse Reaction
BA	Bronchial Aspirate
BAL	Bronchoalveolar Lavage
CM	Concomitant Medication
DMC	Data Monitoring Committee
EC	Ethical Commission
ECG	Electrocardiogram
FAMHP / FAGG	Federal Agency for for medicines and health products
FPFV	First Patient First Visit
GCP	Good Clinical Practice
HSCT	Hematopoietic Stem Cell Transplantation
IAA	Influenza-Associated Aspergillosis
ICF	Informed Consent Form
ICH	International Conference on Harmonisation
IMP	Investigational Medicinal Product
LPLV	Last Patient Last Visit
MIC	Minimal Inhibitory Concentration
PD	Pharmacodynamics
PI	Principal Investigator
PRO	Patient Reported Outcome
SAE	Serious Adverse Event
SAR	Serious Adverse Reaction
SOC	Standard Of Care
SUSAR	Suspected Unexpected Serious Adverse Reaction
TMF	Trial Master File
TSC	Trial Steering Committee
UAR	Unexpected Adverse Reaction

FUNDING AND SUPPORT

Funder	Kind of Financial or Non-Financial Support
MSD	MSD provides posaconazole and partially funds study-related work

CONFLICT OF INTEREST

Investigator	Kind of Conflict of Interest

ROLES AND RESPONSIBILITIES

The Principal Investigator is accountable for the conduct of the trial at his/her site and must ensure adequate supervision of the conduct of the trial at the trial site. If any tasks are delegated, the Principal Investigator must maintain a log ([link](#)) of appropriately qualified persons to whom he/she has delegated specified trial-related duties. The Principal Investigator must ensure that there is adequate and documented training for all staff participating in the conduct of the trial. (It is the Principal Investigator's responsibility to supervise the conduct of the trial and to protect the rights, safety and well-being of the subjects.)

TRIAL SYNOPSIS

Title of clinical trial	A PHASE IV, INTERVENTIONAL, NON-BLINDED, RANDOMIZED CONTROLLED MULTICENTER STUDY OF POSACONAZOLE PROPHYLAXIS FOR THE PREVENTION OF INFLUENZA-ASSOCIATED ASPERGILLOSIS (IAA) IN CRITICALLY ILL PATIENTS
Protocol Acronym	Short Title POSA FLU
Trial Phase	phase IV
Sponsor name	Universitaire Ziekenhuizen Leuven (UZ Leuven)
Coordinating Investigator	[name]. [name], Intensivist, UZ Leuven [name]. [name], Medical microbiologist, UMC Radboud Nijmegen
Contact Adress	UZ Leuven, [name], Belgium
Contact Email	[contact]
Contact [contact]
EudraCT number	2017-003270-14
Other public database nr	
Prinicpal Investigators and Participating Sites	[name]. [name], Intensivist, UZ Leuven [name]. [name], Medical microbiologist, UMC Radboud Nijmegen
Medical condition or disease under investigation	Influenza-associated pulmonary aspergillosis (IAA)
Purpose of clinical trial	Study the effect of antifungal prophylaxis on the incidence of IAA in critically ill patients with severe influenza.
Primary objective	Study if antifungal prophylaxis can decrease the incidence of IAA compared to SOC in critically ill patients with severe influenza pneumonia.
Secondary objective(s)	
Trial Design	Interventional non-blinded randomized controlled multicenter study
Endpoints	The IAA incidence at ICU discharge is the primary endpoint and will be compared in patients receiving posaconazole prophylaxis with those receiving SOC. Secondary outcomes will be time to IAA diagnosis, length of ICU stay, length of hospital stay, 30-day mortality and 90-day mortality
Sample Size	50 patients in each arm
IMP, dosage and route of administration	Posaconazole, 2*300mg/d on day 1, followed by 1*300mg/d from day 2 until day 7, intravenously administrated
Active product(s)	comparator None, SOC
Maximum duration of treatment of a Subject	7 days of prophylaxis

Maximum duration of Trial	4 influenza seasons (the first two influenza seasons will be supported by MSD)
Anticipate First Patient First Visit (FPFV)	Expected 01/12/2017
Anticipate Last Patient Last Visit (LPLV)	Expected 30/03/2021

TRIAL FLOWCHART

Schedule of Events – Trial specific Procedures / Assessments

EVENTS	Screening	Randomization	Treatment Period	ICU discharge	Follow-Up Visits (phone call)
Timing (weeks)		Day 1	Day 2 - ICU discharge		Day 30 and day 90
Informed consent ^a	X				
PCR-confirmed influenza ^b	X				
Inclusion/Exclusion	X	X			
Demographics; Medical history	X				
Symptom directed physical examination	X	X	X	X	
Weight / Height	X				
Vital Signs	X	X	X	X	
Randomization		X			
Microbiology sampling	X	X ^c	X ^d	X	
Chemistry : laboratory measurements	X	X	X	X	
Radiological Assessments (CT / RX)		X	X		
Trial drug administration (max 7 days)		X	X		
IAA mycological evidence ^e	X	X	X	X	X
IAA signs and symptoms assessment	X	X	X	X	
Survival status		X	X	X	X
Adverse event (AE) assessment ^f			→		
Serious Adverse Event (SAE) assessment				→	
Concomitant Medication (CM)					

a: Informed Consent process should take place prior to all other trial-related procedures at the screening visit

b: On NS, BA or BAL within the last 7 days before ICU admission or within 2 days after ICU admission; or based on a positive rapid test if PCR not available

c: BAL GM, BAL culture and serum GM within 48h after influenza diagnosis to collect mycological evidence for IAA-infection

d: BAL GM, BAL culture and serum GM between day 2 after randomization and ICU discharge, at the discretion of the treating physician, or later during ICU admission in case of clinical respiratory deterioration

e: Provided by either (A) a positive culture of *Aspergillus* cultured from BAL, (B) ≥2 positive cultures of *Aspergillus* cultured from a sputum or a bronchial aspirate or (C) a galactomannan (GM) optical density of ≥1 in BAL or ≥0.5 in serum

f: Study drug related adverse events

I Background and Rationale

Invasive aspergillosis has been regarded as an infectious complication of specific immunocompromised patients, which affects a relatively small group of patients. However, in recent years aspergillus disease has become a prominent problem in ICU-patients.

Influenza-associated aspergillosis (IAA) was recently found to be a frequent and severe complication of influenza pneumonia in critically-ill patients.[1] A retrospective observational study during the 2015/2016 influenza season indicated that among 144 patients admitted to the ICUs of all eight Dutch University Medical Centres with influenza, 23 (16%) developed IAA.[2] The underlying diseases in these patients were diverse, and 7 patients had been previously healthy. A 61% mortality rate was observed, including 5 of 7 previously healthy patients who died.[2] It is thus clear that IAA is an early and frequent complication of severe influenza pneumonia, and that delay in diagnosis and treatment increases the probability of death in these critically ill patients. Early diagnosis is difficult due to unspecific clinical and radiological presentation. [1,2]

As influenza virus infection leads to lysis of infected cells, we believe that a severe influenza infection causes cytopathology of the epithelial lining of the trachea and bronchi, providing *A. fumigatus* the opportunity for invasive growth. Many patients developed invasive *Aspergillus* tracheobronchitis, which is a manifestation of invasive aspergillosis that is difficult to diagnose due to lack of specific radiologic features.[3] Furthermore, influenza may contribute to a hyperinflammatory status known as macrophage activation syndrome that contributes to pulmonary damage.[4] Disruption of anatomical barriers and the dysregulated host defense provides an opportunity for *A. fumigatus* to cause fulminant invasive disease. Although biomarkers, such as galactomannan, in BAL and serum are useful tools in diagnosing IAA, early diagnosis proved difficult in the above-mentioned Dutch observational study. Moreover, the median time to initiation of antifungal therapy after influenza diagnosis in survivors and non-survivors was two days versus nine days ($P<0.06$), which underscores that early intervention is critical for survival. Finally, a high azole resistance rate of 29% was observed in these Dutch ICUs, which further complicates patient management.[2,5]

Therefore we propose to perform **an interventional non-blinded randomized controlled multicentric Dutch-Belgian proof-of-concept interventional study** in patients with severe influenza admitted to the ICU, randomizing patients either to oseltamivir therapy with standard care for diagnosis and treatment of secondary infectious complications or to oseltamivir plus posaconazole prophylaxis.

Currently there is no mold-active antifungal agent licensed for prophylaxis of invasive mold disease in ICU patients. The antifungal azole posaconazole is the drug of choice for antifungal prophylaxis in neutropenic patients with acute myeloid leukemia and those with graft-versus host disease following allogeneic HSCT.[6,7] These studies showed that posaconazole prophylaxis reduced the prevalence of invasive aspergillosis to below 2% in these high risk patients. Posaconazole is however not licensed for prophylaxis in other patient groups, i.e. critically ill patients. Based on the experience in patients with hematological

malignancy we anticipate that posaconazole prophylaxis will be effective to reduce the IAA incidence and eventually outcome in patients at risk for IAA.

Although the planned study is a multicenter Dutch-Belgian study, a specific concern in Dutch ICUs is the high rate of azole resistance.[2,8] Although the efficacy of triazoles, including posaconazole, is reduced in experimental models of azole-resistant invasive aspergillosis,[9,10] these animal experiments do indicate that posaconazole prophylaxis is effective to prevent infection due to azole-resistant *A. fumigatus*.[11] Infection was prevented in animals challenged with *A. fumigatus* with a posaconazole MIC of 0.5 mg/l, which represents the vast majority of resistant isolates that are encountered. There is already substantial experience with posaconazole in terms of target PD, toxicity and drug interactions, which will facilitate a rapid implementation into clinical practice if this and future studies demonstrate the efficacy of the intervention.

2 Trial Objectives and Design

2.1 Trial objectives

Our **hypothesis** is that antifungal prophylaxis can reduce the IAA incidence in critically ill patients with influenza pneumonia.

The **objective** of this study is to deliver proof of concept that antifungal prophylaxis in addition to SOC in comparison with SOC alone can reduce the IAA incidence in ICU patients with severe influenza.

2.2 Primary Endpoints

The incidence of IAA-infection at ICU discharge is the **primary endpoint** and will be compared for patients receiving posaconazole prophylaxis with those receiving standard of care.

A patient with **IAA-infection** is defined as a patient having mycological evidence of *Aspergillus* and at least one *Aspergillus* compatible sign or symptom and radiological abnormalities (other than interstitial infiltrates) based on chest CT, or chest X-Ray when CT imaging is not available. Mycological evidence can be provided by either (A) a positive culture of *Aspergillus* cultured from BAL sample, (B) ≥ 2 positive cultures of *Aspergillus* cultured from a sputum or a bronchial aspirate or (C) a galactomannan (GM) optical density of ≥ 1 in BAL or ≥ 0.5 in serum. Galactomannan antigen detection is conducted through sandwich enzyme-linked immunosorbent assay (ELISA) (Platelia Aspergillus; Bio-Rad Laboratories, Marnes-la-Coquette, France) and will be performed according to the instructions of the manufacturer. For the isolation of fungi, lower tract respiratory samples will be inoculated on a Sabouraud agar (2 days at 37°C and another 19 days at 30°). *Aspergillus* species are identified by their culture characteristics and morphologies.

Aspergillus compatible signs or symptoms are defined as at least one of the following:

- Worsening respiratory insufficiency in spite of proper antibiotic and ventilator support
- Dyspnea
- Haemoptysis

- Fever refractory to at least 3 days of appropriate antibiotic therapy. Recrudescent fever after a period of defervescence of at least 48 h while still on AB without apparent cause.

The presence of hyphae in lung biopsy or autopsy are also considered as sufficient evidence for IAA.

An independent review committee, consisting of a clinician and a microbiologist with substantial expertise in invasive fungal infections, will evaluate at the end of the study whether IAA-infection is present, based on the above mentioned criteria.

2.3 Secondary Endpoints

[figure not shown]
Secondary outcomes will be time to IAA diagnosis, length of ICU stay, length of hospital stay, **30-day mortality** and 90-day mortality.

2.4 Trial Design

This study is an interventional non-blinded randomized controlled multicenter study.

- Critically ill patients with PCR-confirmed influenza (for details: see inclusion criteria) are eligible for inclusion in this study and will be randomized to or the posaconazole prophylaxis group or the SOC group. Within 48 hours after influenza diagnosis with a bronchoscopy with BAL (minimum volume of 2x20mL, 0.9% NaCl) and a with a serum galactomannan will be performed as part of routine ICU care in this type of patients. As any bronchoscopy, this bronchoscopy will only be performed if the safety of the patient will not be compromised. If an IAA-infection is suspected based on the result of this BAL ((A) *Aspergillus* cultured from BAL, or (B) a galactomannan (GM) ≥ 1 in BAL or ≥ 0.5 in serum), the patient will be withdrawn from the study and antifungal treatment will be started. The type and duration of antifungal therapy will be at the discretion of the treating physician.
- SOC further includes:
 - The treating physician can decide to perform an additional bronchoscopy with BAL between day 2 after randomisation and ICU discharge in case of respiratory deterioration and clinical suspicion of an IAA-infection. Any bronchoscopy will only be performed if the safety of the patient will not be compromised. In case of positive mycological evidence of an IAA-infection, a CT thorax without IV contrast is performed if possible. If an IAA-infection is documented, antifungal treatment will be started and - in case the IAA-infection is diagnosed before the ending of the study drug - the patient will be withdrawn from the study. Again, type and duration of antifungal therapy will be at the discretion of the treating physician.

- Oseltamivir (non-IMP) will be started at the discretion of the treating physician from the first day of ICU admission as 2*150 mg/day for a duration of 10 days. If oseltamivir had already been started up before ICU admission, oseltamivir treatment will be continued up to a total of 10 days.

*If *Aspergillus* is **only** cultured from sputum (and not from BAL) within the first 48 hours after the influenza diagnosis, the patient will not be withdrawn from the study

3 Trial Medication / Drug

Drug Name	IMP or non-IMP
Posaconazole	IMP

3.1 Investigational Medicinal Product and Dosing Regimen

If a patient is randomized non-blinded to the **posaconazole prophylaxis** group, posaconazole (Noxafil, MSD) will be started intravenously from day 1 of randomization (2*300mg/d on day 1, followed by 1*300mg/d from day 2 for 7 days). Noxafil concentrate injections (vials made of type I glass containing 18mg posaconazole /mL, 300mg posaconazole/vial in total) for intravenous use will be provided by MSD. In both patient groups (prophylaxis and SOC) **oseltamivir** (non-IMP) will be started at the discretion of the treating from the first day of ICU admission as 2*150 mg/day for 10 days. If oseltamivir had already been started up before ICU admission, oseltamivir treatment will be continued up to a total of 10 days.

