3.2 Drug Accountability and Compliance

For each randomized patient 8 drug preparations (posaconazole or placebo) will be delivered by the hospital pharmacy. The amount of used and non-used posaconazole vials will be stated in a drug accountability log.

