5.5.2 Treatment Visits

Day 1 = day of randomization:

- Bronchoscopy with BAL sampling, serum galactomannan (SOC)
- Pregnancy screening negative
- Start study medication
- Gather baseline clinical data including demographic, biochemical, microbiological and radiological data (SOC)

Day 2 – ICU discharge:

- Withdrawal of patients from study if mycological evidence of IAA-infection on BAL of day 1
- Continuation of study medication up to day 7
- Gather clinical data including demographic, biochemical, microbiological and radiological data (SOC)
- Assess presence of IAA-infection (SOC)
- Assess outcome parameters: ICU mortality, IAA-infection (SOC)

30 days after randomization:

Assess outcome parameters: hospital and/or 30-day mortality and a retrospective assessment of IAA-infection (SOC)

90 days after randomization:

- Assess outcome parameters: hospital and/or 90-day mortality and a retrospective assessment of IAA-infection (SOC)

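### Section 3.1, read literally, gives nine posaconazole administrations ending on day 8; the synopsis, flowchart, 5.5.2 and drug supply correspond to eight ending on day 7

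*Combined protocol and SAP*

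**What the plan says.** The course is described in several places in the combined protocol and SAP.

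- Section 3.1 (dosing regimen): two administrations of 300 mg on day 1, "followed by 1*300mg/d from day 2 for 7 days". The same section says that one vial contains 300 mg.
- Trial synopsis, dosage row: "2*300mg/d on day 1, followed by 1*300mg/d from day 2 until day 7". The row for maximum treatment duration gives "7 days of prophylaxis".
- Trial flowchart: the row "Trial drug administration (max 7 days").
- Section 3.2 (accountability): "For each randomized patient 8 drug preparations (posaconazole or placebo) will be delivered by the hospital pharmacy". Used and unused vials go into a log.
- Section 5.5.2 (treatment visits): "Continuation of study medication up to day 7".
- Section 4.4 (withdrawal): the window for withdrawal on an IAA diagnosis is day 1 to day 7 of prophylaxis.
- PK substudy, section 3.3: daily pre-infusion sampling on days without a full curve stops at day 7.

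No passage reconciles section 3.1 with the others, and no order of precedence is given.

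**The concern.** The section headed as the dosing regimen appears to prescribe one administration more, and one day more, than the rest of the protocol allows for. A site working from 3.1 would need a preparation that the pharmacy has not been told to deliver and would go past the stated 7-day maximum. A site working from the synopsis would stop one administration short of 3.1.

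Three operational matters depend on the answer:

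- **Accountability.** Used and unused vials are logged, but a full course could be 8 or 9, so compliance has no single denominator.
- **Withdrawal.** Section 2.4 ties withdrawal for documented IAA to the diagnosis coming before study drug ends, while 4.4 fixes the window at day 1 to day 7. The two agree only if drug ends on day 7.
- **Safety reporting.** Section 6.3.2 collects all adverse events while the patient is on study treatment; after that, only serious events and those of special interest are collected, to 90 days. The change from full to restricted collection moves with the last dosing day.

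**Working it through.** Let k be the number of once-daily administrations starting on day 2. With two administrations on day 1 and no missed days:

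- administrations = 2 + k
- total dose = (2 + k) × 300 mg
- last dosing day = 1 + k

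**The plan's own supply figure (8 preparations, 3.2).** The synopsis runs from day 2 to day 7, so k = 7 − 2 + 1 = 6. Administrations = 2 + 6 = 8. At one 300 mg vial per administration, the synopsis course reproduces the supply figure exactly.

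**Section 3.1, literal reading.** Seven daily administrations counted from day 2 give k = 7. Administrations = 2 + 7 = 9; total = 9 × 300 = 2700 mg; last day = 1 + 7 = 8. The supply figure is not reproduced: 9 − 8 = 1 preparation short.

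**Section 3.1, alternative reading.** If the 7 days cover the whole course including day 1, then k = 6. Administrations = 8, and the conflict disappears. However, the duration in the sentence is attached to the start on day 2, so this is the less natural reading.

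| Source | States directly | Implied k | Administrations | Total | Last day |
|---|---|---|---|---|---|
| 3.1, literal | daily dosing for 7 days from day 2 | 7 | 9 | 2700 mg | 8 |
| Synopsis, dosage | daily dosing on days 2 to 7 | 6 | 8 | 2400 mg | 7 |
| Synopsis, maximum duration; flowchart | 7 days at most | at most 6 | at most 8 | at most 2400 mg | at most 7 |
| 5.5.2 | last day 7 | 6 | 8 (derived) | 2400 mg | 7 |
| 3.2 | 8 preparations | 6 (derived) | 8 | 2400 mg | 7 (derived) |

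Only the synopsis dosage row fixes both the count and the last day. For 5.5.2 the count is derived, and for 3.2 the last day is derived.

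**Size of the discrepancy.** 9 − 8 = 1 administration; 2700 − 2400 = 300 mg; 300 / 2400 = 12.5%; one day. For the 55 patients per arm in section 7.1, if all complete the course, 55 × 8 = 440 vials against 55 × 9 = 495, a difference of 55. For the 50 per arm in the synopsis, the figures are 400 against 450.

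**Boundary check.** Take a patient still on drug whose IAA is diagnosed on day 8 before that day's administration. Under the literal 3.1 course, study drug has not ended, so 2.4 withdraws the patient, but day 8 is outside the 4.4 window. Under the day-7 course, drug has ended and neither rule applies.

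**Primary analysis.** The MITT population in 7.2 requires at least one administration, and the sample size in 7.1 does not use course length. Neither changes with k.

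**The case against.** The strongest reply is that one phrase disagrees with everything else. The synopsis gives a schedule and a last day, two separate entries cap treatment at 7 days, 3.2 gives a matching supply, and 4.4 and the PK substudy name day 7 outright. A site reading the whole protocol would probably notice, and a day-8 administration would breach two stated maxima. The sentence in 3.1 can also be read as 7 days in total.

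Much of this stands, and it limits what can be claimed. Several stronger inferences that a reader might draw are not supported:

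- *That exposure and accountability are undefined.* They are defined, but inconsistently: a supply count, a vial log and a dated schedule all exist.
- *That 3.1 governs, so sites will run out of drug.* The documents give no order of precedence. The shortfall arises only for a site that follows 3.1 literally.
- *That the 4.4 window and the PK sampling days are left open.* Both state day 7. They are further points to align, not gaps.
- *That a ninth administration, or its omission, is a reportable medication error.* Section 6.1.3 lists medication errors without defining them, and nothing says how an extra or missing last administration would be classed.
- *That the efficacy inference is compromised.* The MITT definition and the sample size do not depend on the last dosing day.

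The reply does not remove the conflict. The outlying text is in the dosing section, its literal count differs from the supply, and the reading that would rescue it is stated nowhere. Agreement among the other passages shows where the discrepancy lies; it does not establish which course the sponsor intends.

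**Conclusion.** The point holds as an internal contradiction of limited size. Section 3.1 read literally gives 9 administrations ending on day 8; the synopsis, flowchart, 5.5.2 and supply correspond to 8 ending on day 7. The difference is one administration (300 mg, 12.5% of the shorter course) and one day.

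This rests on three assumptions: that the 7 days in 3.1 are counted from day 2, that one preparation is one 300 mg administration, and that no days are missed. The difference concerns only posaconazole patients still on treatment at the end of the course. Those who die, stop or are withdrawn earlier are unaffected, so 55 patients is a ceiling.

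The consequences are operational: supply and accountability, agreement between 2.4 and 4.4 on when withdrawal applies, and the end of full adverse event collection under 6.3.2. The effect on the primary analysis is negligible. Correction is still worthwhile because sites act on this text.

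**What to change.** The sponsor should state which course is intended and express it once, as a number of administrations and a last dosing day. Section 3.1, the synopsis (dosage and maximum duration), the flowchart, 3.2, 4.4, 5.5.2 and the PK substudy's sampling days should then be brought into line with that statement. The accountability log should use the same count as the full course. The end of study drug referred to in 2.4 and the on-treatment period in 6.3.2 should be tied to the same day, so that withdrawal and adverse event collection have one boundary.

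This review takes no view on which course is right. The cost is protocol wording and, depending on the sponsor's answer, at most one additional vial per posaconazole patient. No analysis or sample size needs to change.
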